2.4.4.1 Analysis of primary efficacy endpoint(s)

Main statistical model and adjustment of covariates

The primary endpoint is the annualized rate of moderate-to-severe AECOPD.

The primary analysis is a modified intention-to-treat analysis. Off-treatment measurements up to the planned treatment durations for patients who prematurely discontinue treatment will be included for the analysis. The planned treatment duration for a patient is from randomization to the earlier of 52 weeks or 24 weeks after the last patient randomized, ie, patients are treated for a minimum of 24 weeks and a maximum of 52.

The observation duration is equal to the planned treatment duration, except when a patient withdraws early from the study, in which case, the observation duration is from randomization to the last contact of the patient within the planned treatment duration. In the primary analysis, all the exacerbation events that happen in the observation duration will be included, regardless if the patient is on treatment or not.

The primary endpoint of the annualized exacerbation rate will be analyzed using a negative binomial regression model. The model will include the total number of events occurring during the observation period as response variable, and the treatment group, the baseline eosinophil strata and region (pooled countries), number of severe COPD exacerbations experienced in previous year (0 vs. 1+) at baseline, smoking history (current vs. former smoker), post-BD FEV1 percent predicted (<50% vs. ≥50%) at baseline as covariates. Log-transformed observation duration will be the offset variable. Parameters will be estimated using the maximum likelihood method with the Newton-Raphson algorithm. The annualized event rate for the two groups and the relative risk ratio for SAR440340 versus placebo with its 95% confidence interval will be estimated from the model.

Sample SAS code is provided below:

```
proc glimmix data=event;  
class eosblgpn trt01pn cntygrln nscopd csmoker ppredFev1;  
model numevents=trt01pn eosblgpn cntygrln nscopd csmoker ppredFev1  
/offset=logdur dist=negbin link=log solution;  
run;
```

If the model fails to achieve convergence, different estimation algorithms will be applied in the order: default→LAPLACE→QUAD. If the issue still exists, other handling may be considered. The adjustment will be added to the footnote of the corresponding outputs. The gross estimates of the annualized event rates will also be presented by treatment group. Mean cumulative function plot will be provided for descriptive purposes.

Similar analysis will be performed for the secondary efficacy population (high EOS group), without the baseline eosinophil strata in the model.

Estimated clinical efficacy of SAR440340 versus placebo

An analysis to assess the efficacy of SAR440340 if patients adhere to the treatment as directed will also be conducted. In this approach, off-treatment measurements of exacerbation events from patients who prematurely discontinue treatment will be excluded from the analysis. Negative binomial model with the same set of covariates as specified in the primary analysis will be used. The offset will be log-transformed on-treatment duration, which is defined as the duration from the first dose to the last dose +14 days within the observation duration. This approach defines the estimand of the efficacy of SAR440340 with treatment adherence. Similar analysis will be performed for the secondary efficacy population (high EOS group), without the baseline eosinophil strata in the model.

Missing data handling

If patients withdraw from the study before completing the planned treatment durations, exacerbation events that may occur after study discontinuation will not be observed. These patients are considered as patients with missing data on exacerbation. Number of patients with missing data, reasons and timing of study withdrawals will be summarized by treatment groups. Summary statistics of selected demographic and baseline disease characteristics will be provided for patients with missing data and patients with complete data separately. Graphical summaries of the dropout patterns such as Kaplan-Meier plots of time to study discontinuation with different reasons of discontinuation may be provided to examine if there is any different missing data pattern between treatment groups. In addition, the following sensitivity analyses will be conducted to assess the robustness of the conclusion of the main model.

- ***Pattern mixture model - multiple imputation (PMM-MI)***

For each patient with missing data of exacerbation events, the number of events that could occur in the period from study discontinuation to the end of planned treatment duration will be estimated based on a negative binomial regression model using observed data with adjustment of the treatment group, region (pooled country), baseline eosinophil strata, number of severe exacerbation events within 1 year prior to the study, smoking history (current vs. former smoker) and post-BD FEV1 percent predicted (<50% vs. ≥50%) at baseline. The period from study discontinuation to the end of planned treatment duration will be the exposure time. Once the number of events in the period is imputed, the total number of events in the planned treatment duration will enter the negative binomial regression model as described in the primary analysis with the offset equal to the log-transformed planned treatment duration.

- ***Control-based PMM-MI***

For each patient with missing data of exacerbation events, the number of events that could occur in the period from study discontinuation to the end of planned treatment duration will be estimated based on the same negative binomial regression model mentioned in the previous bullet point,

except the imputation will be based on the estimate of the control group only. Once the number of events in the residual treatment duration is imputed, similar model as in the PMM-MI will be used.

- ***Tipping point analysis***

For each patient with missing data of exacerbation events, the number of events that could occur in the residual treatment duration will be estimated in a similar fashion as PMM-MI, based on various event rates. If the patient is on SAR440340, the event rate will be increased and if the patient is on placebo, the event rate will not be changed. The adjusted rate will then be used to impute the number of events that would occur in the period with missing data. A sequence of increasing event rates will be used to generate different imputed datasets.

Similar analyses will be performed for the secondary efficacy population (high EOS group), without the baseline eosinophil strata in the model.

Technical details on missing data handling are provided in [Appendix J](#).

Subgroup analysis

To assess the consistency of treatment effects across the subgroup levels, subgroup analyses will be performed for the groups listed below. Within each subgroup, descriptive statistics including number of patients, number of moderate to severe AECOPD, treatment exposure time, annualized rate of moderate to severe AECOPD will be provided by treatment group using the same model as for the primary analysis. Risk ratio between treatment and control and the corresponding 95% CI will be provided within each subgroup. Treatment-by-subgroup interaction and its p-value will be derived by a negative binomial regression model. The model will include treatment, baseline eosinophil strata, region, number of severe COPD exacerbations experienced in previous year (0 vs. 1+) at baseline, smoking history (current vs. former smoker), post-BD FEV1 percent predicted (<50% vs. ≥50%) at baseline, subgroup (if different from the aforementioned covariates) and subgroup-by-treatment interaction.

- Blood eosinophil groups (≥ 150 /mm³ versus <150 /mm³, ≥ 250 /mm³ versus <250 /mm³, ≥ 300 /mm³ versus <300 /mm³) defined by actual lab values
- Blood eosinophil groups (≥ 250 /mm³ versus <250 /mm³) from randomization strata.
- Baseline PARC group (<baseline median versus \geq baseline median)
- Baseline Fibrinogen group (<baseline median versus \geq baseline median)
- Age groups (<65 versus ≥ 65 years)
- Sex (Male, Female)
- Region (East Europe: Poland, Russia, Turkey and Ukraine; Latin America: Argentina and Chile; Western countries: USA, Canada, Australia and Germany)
- Race (White, Non-white)
- Background ICS dose level at randomization (none/low, medium, high)
- Baseline CAT score (below median, equal to or above median)

- Baseline post-BD FEV1 percent predicted (<50% vs. ≥50%)
- Baseline weight (<70, ≥70-<90, ≥90 kg)
- BMI (<25, ≥25-<30, ≥30 kg/m²)
- Smoking history (Current, Former)
- Background therapy (triple versus double)

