5.1 INCLUSION CRITERIA

Participants are eligible to be included in the study only if all of the following criteria apply:

Age

Participant must be 40 to 75 years of age inclusive, at the time of signing the informed consent.

Type of participant and disease characteristics

- I 01. Participants with a diagnosis of COPD for at least 1 year (based on Global Initiative for Chronic Obstructive Lung Disease [GOLD] definition, see (1)).
- I 02. Participants with moderate-to-severe COPD (post-bronchodilator FEV1/forced vital capacity [FVC] <70% and post-bronchodilator FEV1 % predicted <80%, but \geq 30%) at Visits 1 and 2.
- I 03. Participants with COPD Assessment Test (CAT) score \geq 10 at Screening Visit 1 and Visit 2/Randomization.
- I 04. Participants with reported history of signs and symptoms of chronic bronchitis (chronic productive cough for 3 months in the year up to screening in a patient in whom other causes of chronic cough [eg, gastroesophageal reflux, chronic rhinosinusitis, bronchiectasis] have been excluded).
- I 05. Participants with a documented history (eg, medical record verification) of \geq 2 moderate exacerbations or \geq 1 severe exacerbation within the year prior to screening
 - a moderate exacerbation is defined as an AECOPD requiring systemic corticosteroids (oral, intravenous, or intramuscular) and/or treatment with antibiotics (however, use of antibiotics alone does not qualify as a "moderate exacerbation" unless documentation is available that use of antibiotics was necessary for treatment of worsening symptoms of COPD)
 - a severe exacerbation is defined as an AECOPD that required a hospitalization.
- I 06. Participants with Standard of Care background therapy, for 3 months prior to Visit 2/Randomization and at a stable dose for at least 1 month prior to the screening, including either:
 - Double therapy: LABA + LAMA or ICS + LABA or ICS + LAMA.

OR

Triple therapy: ICS + LABA + LAMA.

I 07. Current or former smokers with a smoking history of ≥ 10 packs-year.

Weight

I 08. Body mass index (BMI) ≥ 18.0 kg/m² (inclusive).

Sex

I 09. Male or Female

See [E 28](#) for required contraceptive measures.

Informed Consent

I 10. Capable of giving signed informed consent as described in Appendix 1 ([Section 10.1.2](#)) which includes compliance with the requirements and restrictions listed in the informed consent form (ICF) and in this protocol.

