- Comorbidities (Yes, Ongoing for each): Asthma, Bronchiectasis, Nasal polyps, Chronic sinusitis, Atopic dermatitis, Allergic conjunctivitis, Allergic rhinitis, Food allergy, Hives, Eosinophilic esophagitis, Hypersensitivity to aspirin, Hypersensitivity to NSAID, Atopic disease (Nasal Polyps or Chronic sinusitis or Atopic dermatitis), Allergies (Allergic conjunctivitis or Allergic rhinitis or Food allergy), Hypersensitivity (Hypersensitivity to NSAID or Hypersensitivity to Aspirin)

Disease characteristics at baseline

The following baseline disease characteristics will be summarized by treatment group separately and overall:

- Age at diagnosis of COPD (years)
- Time since diagnosis of COPD at randomization (years)
- Time since last COPD exacerbation at randomization (months)
- Number of moderate or severe COPD exacerbations experienced in the past one year before screening visit (quantitative variable and qualitative variable: 0, 1, 2, 3, ≥ 4)
- Number of moderate COPD exacerbations experienced within 1 year before screening visit (Among the moderate COPD exacerbations, how many required use of (1) systemic corticosteroids and antibiotics, (2) only systemic corticosteroids, (3) only antibiotics. And if systemic corticosteroids were used to treat the moderate COPD exacerbations, the total number of treatment days in the past one year, which will be further broken down to the treatment days using oral, intravenous and intramuscular systemic corticosteroids)
- Number of severe COPD exacerbations experienced within 1 year before screening visit (Among the severe COPD exacerbations, how many required use of (1) systemic corticosteroids and antibiotics, (2) only systemic corticosteroids, (3) only antibiotics. And if systemic corticosteroids were used to treat the severe COPD exacerbations, the total number of treatment days in the past one year, which will be further broken down to the treatment days using oral, intravenous and intramuscular systemic corticosteroids)

- Smoking history (Former, Current), time since cessation of smoking (years) and smoking quantity in pack-years
- Baseline spirometry data including pre-bronchodilator (pre-BD) FEV1 (L), post-bronchodilator (post-BD) FEV1 (L), pre-BD and post-BD FEV1 percent predicted (%), pre-BD and post-BD FEV1/FVC (%), pre-BD and post-BD FVC (L) and pre-BD and post-BD FVC percent predicted (%)
- Baseline COPD Assessment Test (CAT) score
- Baseline Euroqol Questionnaire (EQ-5D-5L) score

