Subgroup analyses of the average change from baseline to Week 16-24 in pre-BD FEV1 will be conducted in the same subgroups as for the primary endpoint based on the primary MMRM model for pre-BD FEV1 described above. Within each subgroup, descriptive statistics including number of patients, mean, SD, and LS means will be provided for each treatment group. Difference in LS means and the corresponding two-sided 95% CI will be provided for the comparison of

SAR440340 and placebo within each subgroup. Treatment-by-subgroup interaction and its p-value will be derived from a MMRM model. The model covariates will include sex, baseline height, smoking history (current vs. former smoker), baseline FEV1 value, treatment group, visit, treatment-by-visit interaction, baseline FEV1-by-visit interaction, the baseline eosinophil strata, region, subgroup (if different from the aforementioned covariates), subgroup-by-treatment interaction, and subgroup-by-treatment-by visit interaction.

2.4.4.2.2 *Change from baseline to Week 24 in post-bronchodilator FEV1*

The analysis method for this endpoint is identical to the analysis of the key secondary efficacy endpoint, the average change from baseline to Week 16-24 in pre-BD FEV1, except that here we only have the value at Week 24, not at Weeks 16 and 20. Similar analysis will be performed for the secondary efficacy population (high EOS group), without the baseline eosinophil strata in the model.

2.4.4.2.3 *Time to first moderate or severe AECOPD*

Time to first moderate or severe AECOPD that occurs from randomization up to week 52 will be analyzed using a Cox regression model with treatment, baseline eosinophil strata and region (pooled countries), number of severe COPD exacerbations experienced in previous year (0 vs. 1+) at baseline, smoking history (current vs. former smoker) and post-BD FEV1 percent predicted (<50% vs. ≥50%) at baseline as covariates. The hazard ratio (HR) between SAR440340 and placebo along with its 95% confidence interval will be estimated by the Cox model. The Kaplan-Meier (K-M) method will be used to estimate the probabilities of first AECOPD at specific time points for each group. P-value from the log-rank test stratified by baseline eosinophil strata and region will be provided.

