Time to first moderate or severe AECOPD is defined as (onset date of the first moderate or severe AECOPD-randomization date+1). If the patient did not experience any moderate to severe AECOPD events, the event time will be considered as censored at date of EOT or the last contact date within the planned treatment duration. Below is sample SAS code for the Cox regression model:

```
proc phreg data=ttevent;  
class trt01pn eosbgpln cntygr1 nscopd csmoker ppredFev1/ param = glm;  
model aval*cnsr(1) = trt01pn eosbgpln cntygr1 nscopd csmoker ppredFev1;  
estimate "SAR440340 vs Placebo"          trt01pn -1 1 / exp;  
ods output Estimates = Estimates;  
  
run;
```

Similar analysis will be performed for the secondary efficacy population (high EOS group), without the baseline eosinophil strata in the model.

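### Optional efficiency improvement: the primary model adjusts for prior severe exacerbations only; adding the collected moderate-or-severe count would change power by about -0.1 to +2 points

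*SAP*

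**What the plan says.** The endpoint counts both moderate and severe events (SAP 2.1.3.1). The primary negative binomial model (SAP 2.4.4.1) adjusts for eosinophil strata, region, smoking, post-bronchodilator FEV1 below 50% predicted, and one history term: "number of severe COPD exacerbations experienced in previous year (0 vs. 1+) at baseline".

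The related exacerbation models use the same kind of term:

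- On-treatment analysis (SAP 2.4.4.1): "Negative binomial model with the same set of covariates as specified in the primary analysis will be used".
- Imputation models (SAP 2.4.4.1): "number of severe exacerbation events within 1 year prior to the study", here without the 0 versus 1+ split.
- Subgroup-interaction model (SAP 2.4.4.1): "The model will include treatment, baseline eosinophil strata, region, number of severe COPD exacerbations experienced in previous year (0 vs. 1+) at baseline".
- Time to first event (SAP 2.4.4.2.3): a "Cox regression model with treatment, baseline eosinophil strata and region (pooled countries), number of severe COPD exacerbations experienced in previous year", with sample code listing "trt01pn eosbgpln cntygr1 nscopd csmoker ppredFev1". SAP 2.4.4.3.3 applies the same approach to the expanded-exacerbation and clinically-important-deterioration endpoints.

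SAP 2.1.1 separately summarizes the number of "moderate or severe COPD exacerbations experienced in the past one year before screening visit (quantitative variable and qualitative variable: 0, 1, 2, 3", with a top category of 4 or more. That count is in none of these models.

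**The concern.** Inclusion criterion I 05 (Protocol 5.1) admits patients with at least two moderate events or at least one "severe exacerbation within the year prior to screening". So every patient with no prior severe event has at least two prior events, and every patient with exactly one prior event has the severe flag set. The flag partly marks the entry route. It cannot separate patients with two prior events from those with three, or four or more.

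The total count matches the endpoint more closely, though not exactly: I 05 defines severe as hospitalization, while the endpoint also counts emergency visits and death. If the count predicts the on-study rate, leaving it out leaves avoidable between-patient variation in the model and a slightly wider confidence interval for the rate ratio. At stake is a little precision.

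**Working it through.** **1. Reproduce the plan's power.** Inputs from SAP 1.3: 170 per arm, dispersion k = 1.5, two-sided 5% Wald test, placebo rate λ of 1.0 to 1.5 per year, 45% reduction, the listed monthly accrual, and drop-out of 9/15/20% by weeks 12/24/52. Exposure t rebuilt from these has mean 35.5 and SD 12.8 weeks, as stated.

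Information per arm = 170 × E[λt/(1 + kλt)]; SE² = 1/I_placebo + 1/I_active; power = Φ(|ln 0.55|/SE − 1.96).

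At λ = 1.0: I = 54.7 and 39.3, SE = √(1/54.7 + 1/39.3) = 0.209, and Φ(0.598/0.209 − 1.96) = 81.5% (stated 81.6%). At 1.2 and 1.5 the results are 85.2% and 88.8%, as stated.

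**2. What the count could explain.** The documents give no distribution or prognostic strength, so both are assumed. Let a share p_x of patients have x prior events, each event multiplying the rate by r. Then CV² = Σp_x r^(2x) / (Σp_x r^x)² − 1. Holding total dispersion at 1.5, the residual dispersion is kc = 2.5/(1 + CV²) − 1.

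With 20/50/20/10% having 1/2/3/4 or more events (base mix) and r = 1.4: CV² = 5.2945/2.1930² − 1 = 0.101 and kc = 2.5/1.101 − 1 = 1.27. At r = 1.2: CV² = 0.0275 and kc = 1.43.

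Averaging the step 1 information over this mix at λ = 1.2 gives 85.3, 85.7, 86.3 and 87.0% at r = 1.1, 1.2, 1.3 and 1.4, against 85.2%. These figures lean high: they treat the dispersion as known, charge no degree of freedom, and credit the existing covariates with none of the variation.

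**3. Fit both models to simulated trials.** Model A is the SAP primary model. Model B adds the count, capped at 4. There were 20,000 trials per setting, with N = 340, λ = 1.2, a 45% reduction and the base mix. The severe flag was assumed in 100/25/35/45% of patients with 1/2/3/4 or more events.

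| Rate ratio per prior event | Power A (%) | Power B (%) | B − A (Monte Carlo SE) | SE ratio B/A |
|---|---|---|---|---|
| 1.0 | 85.2 | 85.1 | -0.13 (0.07) | 1.001 |
| 1.1 | 85.4 | 85.2 | -0.14 (0.09) | 1.000 |
| 1.2 | 85.3 | 85.5 | +0.27 (0.10) | 0.997 |
| 1.3 | 85.4 | 86.0 | +0.60 (0.12) | 0.992 |
| 1.4 | 85.3 | 86.8 | +1.49 (0.14) | 0.986 |

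Power breaks even between 1.1 and 1.2. Type I error is 5.5% for both models at a rate ratio of 1.0. Mean rate-ratio estimates agree within 0.001 in every setting.

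**4. Vary the assumptions at 1.4 per event.**

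- Narrow mix (20/60/15/5), λ = 1.5: 88.7 to 89.4%, +0.64 (SE 0.12).
- Wide mix (30/35/15/20), λ = 1.0: 82.3 to 84.2%, +1.88 (SE 0.16).
- Flag and low FEV1 each prognostic at 1.3, FEV1 correlated with the count: +1.32 (SE 0.14).

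**5. High-eosinophil population** (85 per arm assumed, no eosinophil term): -0.11 (SE 0.11) at 1.0, -0.11 (SE 0.14) at 1.2 and +1.46 (SE 0.18) at 1.4, from about 57% power. Break-even is above 1.2. Over the three mixes the gain at 1.4 is +0.6 to +1.7.

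**6. Cross-check with other inputs.** With 40% of patients having a prior severe event, rate ratios of 1.0 to 1.5, λ of 1.0 and 1.5, and 900 trials per setting, the differences run from -0.3 to +2.1 points (Monte Carlo SE 0.3 to 0.7). The SE ratios run from 1.000 to 0.976.

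**The case against.** **No defect.** The primary model is already adjusted, planned power is 81.6 to 88.8%, and p-values are nominal (SAP 2.4.4.4). One more covariate is a preference. This stands, and it is why the point is optional.

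**The benefit is assumed.** The +2 end comes from a single setting: wide mix, placebo rate 1.0, and 1.4 per event. That strength gives patients in the top category 1.4³ = 2.7 times the rate of patients with one prior event. The simulation also favours the count by making its effect log-linear and its recording exact, whereas I 05 requires documentation only up to the entry threshold. This stands too: the range is conditional on its assumptions and is not a bound.

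**The other models were not tested.** No gain was computed for the Cox, clinically-important-deterioration, imputation or subgroup models. In a Cox model a prognostic covariate changes the conditional hazard ratio and need not narrow its interval. Clinically important deterioration also includes FEV1 and SGRQ changes, for which prior exacerbations are not the natural baseline. This stands, so no quantified benefit is claimed there.

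**Distance from the protocol.** The protocol's primary model has only treatment, eosinophil strata and region, and its allowance for extra covariates is written for FEV1 and time to first event. This carries little weight: the SAP has already added three terms to the primary model, and SAP 1.5 does not list them as modifications.

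**Conclusion.** The primary and on-treatment models represent exacerbation history by a flag that I 05 makes a weak stand-in for total history, while a closer measure is already collected. Adding that measure is a small, optional efficiency improvement. It changes primary-analysis power by about -0.1 to +2 points for assumed strengths of 1.0 to 1.4 per prior event. Break-even lies between 1.1 and 1.2, and above 1.2 in the high-eosinophil population. The result rests on the assumed count mixes, flag rates and prognostic strengths, and on reading the dispersion of 1.5 as the value before covariate adjustment, which the SAP does not specify. The gain may be nil.

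A reader might infer that the omission biases the treatment comparison or leaves the trial short of its stated power. The documents do not support that: treatment is randomized, the power table reproduces, and type I error and rate-ratio estimates are essentially the same with and without the count. Nor do they support a dependable gain across all the exacerbation analyses, since they give no prognostic information and the other models were not evaluated.

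**What to change.** Before unblinding, add one pre-specified term to the primary model in SAP 2.4.4.1: the prior-year number of moderate or severe exacerbations, continuous, with values above 4 set to 4. Keep the severe flag. In the sample code the term belongs in the MODEL statement and not in CLASS. The on-treatment analysis then inherits it.

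For consistency, put the same term in the covariate lists for the imputation and subgroup-interaction models and in the Cox text and code (SAP 2.4.4.2.3), without claiming a gain there. The imputation wording could be aligned with the 0 versus 1+ flag in the same edit. The other time-to-event analyses inherit the change. Appendix J needs none, because it states that its code is explanatory and defers to the main text for covariates.

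The cost is wording in four covariate lists and two code samples, one degree of freedom, and about 0.1 power point if the count is uninformative. No new data are needed.

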
 To evaluate the effects of SAR440340 compared with placebo, on patient reported symptoms and quality of life as documented by e-Diary and utilizing Exacerbations of Chronic Obstructive Pulmonary Disease Tool (EXACT), St. George's Respiratory Questionnaire (SGRQ) and Euroqol-5Dimension (EQ 5D) questionnaire 
 in all patients treated with SAR440340/placebo in subpopulations with high blood eosinophil level (≥ 250 /mm³) and low blood eosinophil level (<250 /mm³) 	
 Change from baseline in the EXACT scores at Week 24 Change from baseline in the SGRQ scores at Week 24 Change from baseline in the EQ-5D scores at Week 24

 To evaluate the pharmacokinetic (PK) profile of SAR440340 in serum 	
 Serum functional SAR440340 concentrations

 To evaluate the effects of SAR440340 Antidrug antibodies (ADA) 	
 Antidrug antibodies (ADA) against SAR440340

 To evaluate the effects of SAR440340 compared with placebo, on FEV1, AECOPD, and other relevant endpoints 
 in subpopulations with high blood eosinophil level (≥ 250 /mm³) and low blood eosinophil level (<250 /mm³) in subpopulations according to use/no use of ICS 	
 Change from baseline to Week 24 in FEV1 (pre-bronchodilator and post-bronchodilator) Rate of moderate-to-severe AECOPD

Objectives	Endpoints
with bronchodilators as background therapy, fibrinogen levels, and smoking status.	

 To evaluate the effects of pharmacogenomics on SAR440340 	
 Future Assessment of DNA or RNA samples for the pharmacogenomics sub study to identify genomic associations with clinical or biomarker response, other clinical outcome measures and possible AEs

 To evaluate the effects of SAR440340 compared with placebo on other respiratory assessments (expanded AECOPD endpoint) 	
 Change from baseline to Week 16-24 in FVC (% predicted and absolute values in mL). Time to the first moderate and severe exacerbations or time to study drug discontinuation (after Week 4) due to lack of efficacy, based on the investigator's judgement (expanded AECOPD endpoint)

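### Eosinophils, PARC, fibrinogen and CAT are tested as effect modifiers only as two-level groups; adding one continuous interaction per marker would be a cheap gain if the effect is gradual

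*SAP*

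**What the plan says.** The subgroup part of SAP 2.4.4.1 gives its purpose as "To assess the consistency of treatment effects across the subgroup levels". For each factor it plans an interaction test: "Treatment-by-subgroup interaction and its p-value will be derived by a negative binomial regression model". The four markers enter that test as follows.

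- **Eosinophils:** two groups at each of three fixed cuts (150, 250 and 300 /mm³), the last being "≥ 300 /mm³ versus <300 /mm³) defined by actual lab values", and again by the 250 /mm³ randomization stratum.
- **PARC:** "Baseline PARC group (<baseline median versus" at or above it.
- **Fibrinogen:** "Baseline Fibrinogen group (<baseline median versus" at or above it.
- **CAT:** "Baseline CAT score (below median, equal to or above median").

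SAP 2.4.4.2.1 carries this over to pre-bronchodilator FEV1: the analyses "will be conducted in the same subgroups as for the primary endpoint".

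Protocol Table 1 lists, as exploratory objectives, effects in subpopulations with eosinophils above and below 250 /mm³ and by ICS use, "fibrinogen levels, and smoking status". SAP 2.4.4.4 makes all p-values nominal. Neither document claims any power for an interaction.

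**The concern.** All four markers are measured on a continuous or near-continuous scale, and no treatment-effect analysis in either document uses the measured values. A two-level split treats a patient just above the cut like one far above it. If benefit rises gradually with the marker, the split discards part of the evidence for that.

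The documents give no biological or design reason for the median cuts of PARC, fibrinogen and CAT. A result tied to this sample's median is also hard to carry into a later trial. The 250 /mm³ cut is different: it is the stratification threshold, with enrolment steered to about half the patients on each side.

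At stake is how much a proof-of-concept trial of 340 patients can say about which patients respond, which for eosinophils and fibrinogen is a listed exploratory objective. The primary and key secondary treatment comparisons are not affected.

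**Working it through.** **Inputs from SAP 1.3.** 170 patients per arm; placebo rate 1.0 to 1.5 per year; dispersion k = 1.5; two-sided 5% Wald test; the stated monthly accrual; 24 to 52 weeks of treatment; drop-out of 9%, 15% and 20% by 12, 24 and 52 weeks. FEV1: SD 0.3 L, 15% missing.

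**Assumptions not in the documents.** The marker is normal on the scale where the log rate ratio is linear. It has no prognostic effect. The rate ratio changes 1.5- to 3-fold between −1 SD and +1 SD.

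**Step 1: the plan's own figures.** Var(log rate ratio) = sum over arms of 1 / (170 × E[μ/(1 + kμ)]), where μ is rate × individual exposure. Exposure built from accrual and drop-out has mean 35.5 weeks and SD 12.8, as stated. For a 45% reduction the standard errors are 0.2089, 0.199 and 0.1882 at placebo rates 1.0, 1.2 and 1.5. Power is Φ(0.598/SE − 1.96) = 81.6%, 85.2% and 88.8%, equal to the SAP table.

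**Step 2: continuous against median split.** Let b be the slope of the log rate ratio per marker SD, so b = ln(fold)/2.

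- Continuous: the slope's SE is about the main-effect SE, so z = b/SE.
- Median split: the halves differ by 2 × 0.798 SD in mean marker, and the SE of the difference between halves is 2 × SE. So z = 0.798 × b/SE.
- Information kept: 0.798² = 2/π = 64%.

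Example (2-fold, rate 1.0): b = 0.347 and z = 0.347/0.2089 = 1.66, giving Φ(−0.30) = 38.2%. With the split, z = 1.32, giving Φ(−0.64) = 26.2%.

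| Fold change, −1 SD to +1 SD | Rate 1.0: continuous / split | Rate 1.5: continuous / split | Loss over rates 1.0 to 1.5 (points) |
|---|---|---|---|
| 1.5 | 16.1% / 11.8% | 18.9% / 13.6% | 4.3 to 5.3 |
| 1.75 | 26.7% / 18.6% | 31.8% / 22.0% | 8.1 to 9.8 |
| 2 | 38.2% / 26.2% | 45.3% / 31.2% | 11.9 to 14.1 |
| 2.5 | 59.2% / 41.7% | 68.2% / 49.3% | 17.5 to 18.9 |
| 3 | 74.8% / 55.5% | 83.1% / 64.4% | 18.7 to 19.4 |

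**Step 3: simulation.** 1200 trials per setting, maximum-likelihood negative binomial fits, rate 1.2, average rate ratio 0.55. Continuous against split: 30.2% / 20.9% (1.75-fold), 40.1% / 29.0% (2-fold), 61.2% / 47.0% (2.5-fold) and 75.9% / 57.9% (3-fold). With no interaction the rejection rates were 5.6% and 5.8%.

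**Step 4: the reverse case.** If the effect is a step at the median, the split is the better test. A 2-fold step at rate 1.2 gave 26.7% (continuous) against 36.8% (split). A second set of simulations (700 trials per setting, rates 1.0 and 1.5) gave continuous-test deficits from 22 − 16 = 6 points to 70 − 49 = 21 points.

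**Step 5: FEV1.** The overall SE is 0.3 × √(2/144.5) = 0.0353 L, with 144.5 = 170 × 0.85. This gives 1.96 × 0.0353 = 0.07 L, the plan's least significant difference. Assume effects of 0.18 L and 0.06 L in the two halves. Split: z = 0.12/(2 × 0.0353) = 1.70, power 40%. Continuous: z = 1.70 × √(π/2) = 2.13, power 57%.

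**Not computed.** The loss at 150 and 300 /mm³ depends on where those cuts fall in the eosinophil distribution, which the documents do not give.

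**The case against.** The strongest reply is that the plan does what it sets out to do. The stated purpose is consistency across subgroup levels, the eosinophil objectives are themselves worded as above and below 250 /mm³, p-values are nominal, and no interaction power is promised. PARC and CAT appear in no subgroup objective: PARC is listed as a pharmacodynamic measure, and CAT is collected only for eligibility. All of this stands, and it is why the point is an optional addition.

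The fixed eosinophil cuts are reusable thresholds, and 250 /mm³ has a design basis. That stands too; the complaint about sample medians applies only to PARC, fibrinogen and CAT.

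A median split is unaffected by monotone rescaling and robust to outliers, whereas a slope needs a sensible scale. This stands and shapes the fix. For modest gradients even the continuous test is weak: at 1.5-fold, which around a 45% overall reduction means about 53% against 35% in the two halves, it has 16% to 19% power.

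A reader might infer that the SAP never uses marker values at all. It does: baseline values, and changes over time, are summarized descriptively (SAP 2.1.1 and 2.4.6.2). Protocol 9.4.3 also says pharmacodynamic analyses will be presented apart from the main report, so further modelling elsewhere cannot be excluded. The gap is in treatment-effect analyses in these two documents.

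**Conclusion.** The point holds as a low-cost improvement. Effect modification by the four markers is tested only as two-level groups. Under a linear effect in a roughly normal marker, a median split costs about 4 to 19 points of interaction power across 1.5- to 3-fold gradients. Those gradients are assumptions.

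Two stronger readings are tempting. One is that the cuts cost a fixed amount of power for every marker. The documents do not support this: they give neither an interaction size nor the eosinophil distribution, so nothing can be stated for 150 and 300 /mm³. The other is that the cuts are wrong and should go. They are the better choice if the true effect is a step at the cut, by about 6 to 21 points, and nothing in the documents says which shape is true. No stated figure or error rate in the plan is in error.

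**What to change.** Keep all categorical subgroup analyses as written. Before unblinding, add to SAP 2.4.4.1 one exploratory treatment-by-marker interaction for each of the four markers, with the marker as a continuous covariate (main effect plus interaction) in the same negative binomial model. In SAP 2.4.4.2.1, add the same interaction on the Week 16-24 contrast of the FEV1 MMRM.

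- **Scale:** log for eosinophils and PARC; fibrinogen and CAT on their own scale.
- **Edge cases:** prespecify an offset for zero eosinophil counts, and use LLOQ/2 for values below LLOQ, as SAP 2.4.6.2 already does for biomarkers.
- **Report:** the nominal p-value, and the estimated rate ratio or FEV1 difference with 95% CI at the 10th, 25th, 50th, 75th and 90th percentiles of the marker.

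The cost is a few lines of text and 4 markers × 2 endpoints = 8 model fits on data already collected. The downside is about eight more nominal p-values and a linearity assumption, which readers can check against the retained categorical results.
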